# 5.3 Randomization and Blinding

Participants who meet all eligibility criteria will be randomized into the study. Participants will be randomized in a 1:1:1 ratio to receive combination therapy (obicetrapib 10 mg + ezetimibe 10 mg [administered as one 10 mg obicetrapib tablet and one 10 mg ezetimibe capsule]), obicetrapib monotherapy (obicetrapib 10 mg [administered as one 10 mg obicetrapib tablet and 1 placebo capsule]); or placebo (administered as 1 placebo tablet and 1 placebo capsule).

At randomization, participants will be stratified according to their Screening Visit LDL-C level (≥100 or <100 mg/dL). An automated interactive response technology (IRT) system will be used to assign the participant to 1 of the 3 treatment groups.

Participants, Investigators, the CRO, and the Sponsor will be blinded to all lipid results from Day 1 (Visit 2) for the first participant until all enrolled participants complete the Day 84 (End of Treatment) visit or are withdrawn from the study, in order to protect blinding to treatment assignment.

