## 9.2.5 Sample Size Determination

A sample size of at least 108 evaluable participants (ie, 36 participants per treatment group) will provide >90% power to detect a 30% difference in LDL-C reduction at Day 84 (SD of 15%) for each of the obicetrapib treatment groups compared with the placebo group at a 1-sided significance level of 0.025.

The sample size for this study was determined in order to provide sufficient power for the analyses of the primary and first secondary efficacy endpoints described in Section 7.1. Therefore, assuming an approximately 5% dropout rate, enrollment of approximately 114 participants (ie, 38 participants per treatment group) is planned for this study. This sample size will also contribute sufficient participant exposure and safety data.

Participants will be stratified according to their Screening Visit LDL-C levels ( $\geq 100 \text{ or } < 100 \text{ mg/dL}$ ).

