2.2 Study Design

2.2.1 Overview

This study is a placebo-controlled, double-blind, randomized, Phase 2 study to evaluate the efficacy, safety, and tolerability of obicetrapib 10 mg, both in combination with ezetimibe 10 mg and as monotherapy, as an adjunct to high-intensity statin therapy.

Approximately 114 eligible participants (38 participants per treatment group) will be randomized in a 1:1:1 ratio to 1 of the following treatment groups:

- Combination therapy: Obicetrapib 10 mg + ezetimibe 10 mg (administered as one 10 mg obicetrapib tablet and one 10 mg ezetimibe capsule);
- Obicetrapib monotherapy: Obicetrapib 10 mg (administered as one 10 mg obicetrapib tablet and 1 placebo capsule); or
- Placebo (administered as 1 placebo tablet and 1 placebo capsule).

Randomization will be stratified according to LDL-C levels (≥ 100 or < 100 mg/dL).

During the 12-week Treatment Period, the assigned study drugs will be administered by the participants, once daily on Day 1 to Day 84 at approximately the same time each morning. Participants will return to the site on Day 28 (± 2 days), Day 84 (± 2 days) and Day 112 (± 2 days) for efficacy, safety, and pharmacokinetic (PK) assessments. Participants, Investigators, and the Clinical Research Organization (CRO), and the Sponsor will be blinded to all lipid results from Day 1 (Visit 2) for the first participant until all enrolled participants complete the Day 84 (End of Treatment [EOT]) visit or are withdrawn from the study, in order to protect blinding to treatment assignment.

Participants will return to the site for a Safety Follow-Up (FUP) Visit (Day 112; Visit 5) approximately 4 weeks after the end of the Treatment Period for safety and PK assessments.

Refer to [Table 1 Schedule of Procedures](#) for further details.

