3.4.1 Primary Efficacy Endpoints

Primary Analysis

The primary efficacy endpoint is the percent change from Day 1 to Day 84 in LDL-C (as determined by approach 1 above) for the combination treatment group compared to the placebo group. The percent change will be calculated from Day 1 (Baseline) to each measurement taken at Day 28 and Day 84.

The percent change in LDL-C from Day 1 to Day 84 for each treatment group is defined mathematically as μ_j , where j stands for the j^{th} treatment ($j=0,1,2$) and the subscript 0 refers to the placebo group. The hypotheses testing to the percent change in LDL-C from Day 1 to Day 84 is then defined statistically as following:

$$H_0: \mu_j - \mu_0 = 0, H_1: \mu_j - \mu_0 \neq 0, \text{ where } j=1,2$$

LDL-C values will be summarized by visit and treatment group; visit values, change from baseline and percent change from baseline will be summarized. Missing data patterns in the LDL-C values will also be summarized by treatment group.

The analysis of the percent change from Day 1 to Day 84 in LDL-C will be performed using a mixed model for repeated measures (MMRM) approach. The analysis will include fixed effects for treatment, visit, and treatment-by-visit interaction, along with a covariate of the baseline value as a continuous covariate. Randomization was stratified according to Screening Visit LDL-C value (≥ 100 or < 100 mg/dL) to ensure a similar distribution of LDL-C values across all treatment groups. However, the MMRM model will include the original scale of the baseline LDL-C values as continuous covariate.

The Restricted Maximum Likelihood estimation approach (REML) will be used with an unstructured covariance matrix. The least-squares means (LSMean), standard errors, and 2-sided 95% confidence intervals for the combination treatment group and for the comparison of the combination treatment group to the placebo group will be provided.

The MMRM approach will include all available assessments of percent change in LDL-C from Day 1 to Day 28 and Day 84. The model assumes that the data are missing at random (MAR). If any data are missing, the model will use all information from the other time points to estimate the mean treatment difference at the given time point. No imputation of missing data will be performed for the primary analysis.

The primary analysis will be conducted for the mITT, ITT, and PP Populations.

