The analysis will be implemented using SAS® Proc Mixed. The sample SAS code can be found below:

```
*****
```

Note:

USUBJID = unique subject identifier

TREATMENT = 0 (Placebo), 1 (Obicetrapib monotherapy), 2 (Combination therapy)

VISIT = visit

BASE = Baseline value

PCHG = Percent change from Baseline

```
*****
```

proc mixed;

class USUBJID TREATMENT VISIT;

model PCHG = TREATMENT BASE VISIT TREATMENT*VISIT / solution cl;

Repeated VISIT / TYPE=UN sub=USUBJID;

lsmeans VISIT*TREATMENT / cl diff;

run;

```
*****
```

Sensitivity Analyses

Four sensitivity analyses will be performed for the primary efficacy endpoint:

1. MMRM with imputation
2. Analysis of Covariance (ANCOVA)
3. ANCOVA using LDL-C by PUC only
4. MMRM (no imputation) using LDL-C by Martin/Hopkins Calculation

All sensitivity analyses will be conducted on the mITT Population.

Sensitivity Analysis 1

The first sensitivity analysis will impute missing data using a control-based pattern imputation model assuming the data are missing not at random (MNAR). The multiple imputation will be performed such that only observations from the placebo group are used to derive the imputation model for missing LDL-C values. Missing data at Day 28 and 84 will be imputed using multiple imputation methodology in two steps. Initially, 25 data sets will be imputed for non-monotone missing values in the original dataset. In the second step the remaining monotone missing values will be imputed. Upon completion of the trial, if the percentage of cases with incomplete data is larger than initially anticipated then the number of imputations will be increased for the final analysis.

The variables for the imputation model will consist of LDL-C values from baseline and Days 28 and 84. For each imputation dataset, the percent change from baseline to Day 84 will be analyzed using the MMRM model described above for the primary analysis. The results from these 25 analyses will be combined using Rubin's method to construct the treatment estimates using the parameter estimates and associated standard errors. Similarly, the difference of the adjusted treatment means (combination treatment – placebo) will be presented with the associated standard error and 95% confidence interval. Randomly chosen seed numbers will be selected for the analysis and will be retained.

Example SAS code to create a dataset for non-monotone missing values is shown below:

```
*****
```

Note:

non-MONOTONE missing values

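### The primary model leaves out Screening LDL-C, a second pre-treatment value every participant has; adding it would narrow the interval modestly

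*SAP*

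**What the plan says.** Protocol 5.3 states that "participants will be stratified according to their Screening Visit LDL-C level", with the cut at 100 mg/dL. SAP 3.4.1 repeats this and gives the purpose as balance across arms. It then sets the stratum aside: "However, the MMRM model will include the original scale of the baseline LDL-C values as continuous covariate". The sample code agrees with the text: "model PCHG = TREATMENT BASE VISIT TREATMENT*VISIT / solution cl".

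SAP 3.1.3 defines baseline as the last value before the first dose, which is normally the Day 1 sample. The Screening sample is taken between Day -14 and Day -1 (Protocol Appendix A). It exists for every eligible participant, because inclusion criterion 3 (Protocol 4.1) requires a fasting LDL-C above 70 mg/dL at that visit.

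The ANCOVA sensitivity analyses (2 and 3) adjust for treatment and baseline LDL-C only. Sensitivity analyses 1 and 4 reuse the primary MMRM. The logistic models in SAP 3.4.3 contain treatment and baseline LDL-C. No planned efficacy model contains Screening LDL-C or the stratum.

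**The concern.** The SAP offers continuous baseline LDL-C in place of a two-level cut. A continuous covariate does carry more than a dichotomy of the same measurement, but these are different measurements: the stratum comes from the Screening draw and the covariate from the Day 1 draw.

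The outcome makes this matter a little more than usual. Percent change has Day 1 LDL-C in its denominator, so error in that one draw passes into every participant's outcome, and adjusting for the same noisy value corrects it only in part. Screening LDL-C measures the same pre-treatment level with separate error. It is unaffected by treatment and already in the database.

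At stake is the width of the interval for the primary contrast (combination versus placebo) and the first secondary contrast (monotherapy versus placebo).

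**Working it through.** **1. The plan's own figures.** Protocol 9.2.5 gives 36 evaluable per arm, a difference of 30 points and SD 15, "compared with the placebo group at a 1-sided significance level of 0.025". This matches the two-sided 95% intervals in SAP 3.4.1.
- SE of a difference: 15 × √(2/36) = 3.54.
- Noncentrality: 30/3.54 = 8.49, so power exceeds 99.99%. This is consistent with the stated figure of more than 90%.
- Dropout of 5%: 36/0.95 = 37.9, rounded up to 38 per arm; 108/0.95 = 113.7, rounded up to 114. Both reproduce.
- 95% half-width on 70 degrees of freedom: 1.994 × 3.54 = 7.05 points.

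**2. What a further covariate buys.** If r is its partial correlation with the outcome, given treatment and Day 1 LDL-C, the SE is multiplied by √(1 − r²).

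| Partial r | SE change | Half-width |
|---|---|---|
| 0.1 | −0.5% | 7.02 |
| 0.2 | −2.0% | 6.91 |
| 0.3 | −4.6% | 6.73 |
| 0.4 | −8.3% | 6.46 |

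The documents give no figure from which r can be derived.

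**3. Simulation under stated assumptions.** Each setting had 1,500 three-arm trials with 36 per arm, stratified allocation and Screening LDL-C above 70 mg/dL. Day 84 percent change was analysed by ANCOVA. Between-person CV was 20% or 30% and within-person CV 4% to 13.5%. The spread of individual response was lowered from 0.14 to 0 as within-person CV rose, to hold the residual SD near 15 (14.2 to 15.1). Entries are for between-person CV 20% / 30%; SE changes are in the model SE, and half-widths are scaled from 7.05.

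| Within-person CV | Stratum alone | Screening LDL-C | Half-width with Screening LDL-C |
|---|---|---|---|
| 4% | +0.2% / +0.2% | −0.5% / −0.6% | 7.01 / 7.01 |
| 6% | −0.2% / −0.1% | −1.8% / −2.0% | 6.93 / 6.91 |
| 8% | −0.9% / −0.5% | −2.9% / −3.2% | 6.85 / 6.82 |
| 10% | −1.8% / −1.2% | −4.4% / −5.2% | 6.74 / 6.68 |
| 12% | −3.1% / −2.1% | −6.1% / −7.1% | 6.62 / 6.55 |
| 13.5% | −3.2% / −2.6% | −6.1% / −7.9% | 6.62 / 6.49 |

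- In terms of participants, the Screening LDL-C gain runs from 1/0.995² = 1.01 to 1/0.921² = 1.18, or about 1% to 18% more effective sample size.
- The actual spread of the estimates across simulated trials fell by 0.8% to 6.0% with Screening LDL-C.
- With the stratum alone, that spread changed by less than 1% in 11 of the 12 settings and fell by 1.7% in the other.
- Adding the stratum on top of Screening LDL-C raised the model SE by 0.2 to 0.4 points of its ratio, so it gave nothing further.

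**4. Does a single-visit ANCOVA mislead?** A check with the planned two-visit structure used unstructured covariance, complete data, within-person log SD 0.08 to 0.15, between-person 0.20 to 0.30 and response log SD 0.10. Screening LDL-C cut the model SE by 4.0% to 5.8% and the empirical SE by 3.1% to 6.8%. Both lie inside the range above.

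**The case against.** The strongest reply is that nothing here is an error. Protocol 9.2.1.1 pre-specifies the same model, and the SAP names the stratification and says openly what replaces it. Preferring a continuous lipid value to a two-level cut is a defensible choice. Power is above 99.99% with or without the change. The size of the gain is also not anchored in the documents, and it depends heavily on the spread of individual drug response. Over similar within- and between-person variability, the gain is about 5% to 7% with a response log SD of 0.10 and about 2% to 4% with 0.30.

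All of that stands. It limits the point to an optional improvement in precision and rules out any narrow percentage. It does not answer why a second pre-treatment measurement should go unused, since Day 1 LDL-C is not the variable that defined the strata.

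A reader might go further and infer that omitting the randomisation factor makes the analysis invalid or its intervals too short. The documents and the calculations do not support this. In every setting with within-person CV of 8% or more, adding the stratum lowered the model SE by more than it lowered the actual spread of the estimates. Leaving it out therefore errs, if at all, towards a wider interval. Nor is there a conflict between protocol and SAP.

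A reader might also take the stratum itself as the main remedy. On these figures almost all of the gain comes from the continuous Screening value.

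**Conclusion.** The point holds as a minor improvement. The primary MMRM adjusts for one pre-treatment LDL-C value when two are available, and the one it uses is also the denominator of the outcome. Adding continuous Screening LDL-C lowered the SE in every setting tried, by roughly 0.5% to 8%. At SD 15 and 36 per arm that takes the half-width from 7.05 to between about 7.0 and 6.5 points.

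The direction is consistent. The size is an assumption, resting on within-person CV of 4% to 13.5%, between-person CV of 20% to 30% and a residual SD near 15. The stratum alone is worth about 0% to 3% in model SE, mostly under 1% empirically, and nothing once Screening LDL-C is included. The planned analysis remains valid, and its power and likely conclusion do not change.

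**What to change.** - **Primary MMRM (primary and first secondary contrasts) and ANCOVA sensitivity analysis 2:** add continuous Screening LDL-C beside Day 1 LDL-C. Define it as the last qualifying screening value, the one used by the IRT for stratification, because Protocol 4.3 and 4.4 allow retests and rescreening.
- **ApoB secondary endpoints:** add Screening ApoB beside baseline ApoB. The lipid profile is drawn at Screening (Protocol Appendix A) and includes ApoB (Appendix B).
- **Sensitivity analysis 3 (PUC):** Screening LDL-C may be added, but only as an auxiliary covariate. Universal PUC is planned at Visits 2 and 4 only. The eligibility limits (LDL-C above 70 mg/dL, TG below 400 mg/dL) keep qualifying Screening values outside the PUC triggers, so these are generally Friedewald values.
- **Stratum:** optional, for consistency with the randomisation, and not presented as a gain in precision.

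The cost is one degree of freedom and about one line of SAP text and code, plus the definition of the Screening value. No new data or visits are needed. The change should be made before unblinding. If the sponsor prefers to keep the primary model as it is, the same model could be added as a pre-specified sensitivity analysis.

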In the second sensitivity analysis, the percent change from Day 1 to Day 84 in LDL-C (as determined by approach 1 above) for the combination treatment group compared to the placebo group will be analyzed using an ANCOVA model with fixed effects of treatment group and the baseline LDL-C value as a continuous covariate. The least squares means, standard errors, and 2-sided 95% confidence intervals for the combination treatment group and for the comparison of the combination treatment group to the placebo group will be provided. The treatment comparison (combination treatment – placebo) will be performed using a 2-sided test at the $\alpha = 0.05$ level of significance. No imputation of missing data will be performed for this sensitivity analysis.

Example SAS code can be found below:

```
*****
Note:
USUBJID = unique subject identifier
TREATMENT = 0 (Placebo), 1 (Obicetrapib monotherapy), 2 (Combination therapy)
BASE = Baseline value
PCHG = Percent change from Baseline
*****
proc glm data=LDL_C;
  class TREATMENT;
  model PCHG = TREATMENT BASE / ss1 ss3;
  means TREATMENT;
  lsmeans TREATMENT / cov stderr pdiff cl;
  estimate "Combination - Placebo"      TREATMENT -1 0 1;
run;
*****
```

Sensitivity Analysis 3

In the third sensitivity analysis, the percent change from Day 1 to Day 84 in LDL-C will be assessed where the LDL-C values will be measured by PUC. The percent change from Day 1 to Day 84 in LDL-C by PUC for the combination treatment group compared to the placebo group will be analyzed using an ANCOVA model similar to the model described in the second sensitivity analysis. No imputation of missing data will be performed for this sensitivity analysis.

Sensitivity Analysis 4

In the fourth sensitivity analysis, the percent change from Day 1 to Day 84 in LDL-C will be assessed where the LDL-C values will be derived using the Martin/Hopkins calculation. A similar MMRM model as described for the primary analysis will be used.

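### The primary MMRM holds the baseline LDL-C slope equal at Day 28 and Day 84; adding a baseline-by-visit term is a small, nearly free improvement

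*SAP*

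**What the plan says.** SAP 3.4.1 specifies "fixed effects for treatment, visit, and treatment-by-visit interaction, along with a covariate of the baseline value as a continuous covariate", fitted by REML. The code agrees: "model PCHG = TREATMENT BASE VISIT TREATMENT*VISIT / solution cl", with "Repeated VISIT / TYPE=UN sub=USUBJID" for the covariance. Protocol 9.2.1.1 gives the same fixed effects. No baseline-by-visit term appears in any of the three places.

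The model has two post-baseline visits: "The MMRM approach will include all available assessments of percent change in LDL-C from Day 1 to Day 28 and Day 84".

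Two other parts of SAP 3.4.1 bear on the point. Randomization was stratified on Screening LDL-C (≥100 or <100 mg/dL) "to ensure a similar distribution of LDL-C values across all treatment groups". In Sensitivity Analysis 2, the Day 84 percent change "will be analyzed using an ANCOVA model with fixed effects of treatment group and the baseline LDL-C value as a continuous covariate", so that analysis estimates a slope from Day 84 data alone.

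**The concern.** Baseline LDL-C is both the covariate and the denominator of percent change. How strongly percent change depends on it is set by how closely the later value tracks Day 1, and that may not be the same after 4 weeks as after 12. The model lets the treatment effect and the variance differ by visit but not this slope, and the documents give no reason for the restriction.

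Two things are at stake. First, any chance baseline difference between arms is corrected at Day 84 with a slope that draws on Day 28 data. Second, the primary estimate and the Day 84 ANCOVA will differ even if nobody has missing data. With about 5% dropout planned, a reader could mistake that gap for a missing-data effect.

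**Working it through.** **1. The plan's own figures.** Protocol 9.2.5: "A sample size of at least 108 evaluable participants (ie, 36 participants per treatment group"), difference 30 points, SD 15, one-sided 0.025, 5% dropout.

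- SE of a Day 84 difference: 15 × √(2/36) = 3.54 points.
- Standardized effect: 30 / 3.54 = 8.49, so power is above 99.99%, consistent with the stated >90%.
- Enrolment: 108 / 0.95 = 113.7, rounded up to 114, as stated.

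**2. What the common slope does.** Let Δ be the baseline difference between combination and placebo, and b28 and b84 the within-arm slopes at each visit. With complete data:

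- Planned model: Day 84 contrast = raw difference − b_c × Δ, where b_c = w28·b28 + (1 − w28)·b84.
- With `BASE*VISIT`: Day 84 contrast = raw difference − b84 × Δ, which is exactly the Day 84 ANCOVA.
- The two differ in size by w28 × |b84 − b28| × |Δ|.

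The weight is w28 = (σ84² − c) / (σ28² + σ84² − 2c), where c is the residual covariance between visits. The documents give none of these, so assumed values:

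- SD 15 at both visits: w28 = 0.50 at any correlation.
- SD 12 and 15, correlation 0.7 (c = 126): w28 = (225 − 126) / (144 + 225 − 252) = 99/117 = 0.85.
- SD 12 and 15, correlation 0.8 (c = 144): w28 = 81/81 = 1.00.

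So if Day 28 is the less variable visit, the Day 84 contrast may be adjusted almost wholly with the Day 28 slope.

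**3. How different the slopes might be.** If the untreated LDL-C mean (assumed 95 mg/dL) and SD are constant over visits, the placebo slope is roughly (100/95) × (r − 1), where r is the correlation with Day 1. Active-arm slopes scale by the fraction of LDL-C remaining. For assumed effects of −45% and −58%, the average factor is (1 + 0.55 + 0.42)/3 = 0.657.

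| r at Day 28 → Day 84 | Average slope difference, points per mg/dL |
|---|---|
| 0.75 → 0.70 | (100/95) × 0.05 × 0.657 = 0.03 |
| 0.8 → 0.6 | (100/95) × 0.20 × 0.657 = 0.14 |
| 0.8 → 0.5 | (100/95) × 0.30 × 0.657 = 0.21 |

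**4. Size by hand.** Under simple randomization with an assumed baseline SD of 20, the SE of Δ is 20 × √(2/36) = 4.71 mg/dL. With w28 = 0.5, a slope difference of 0.2 and a 2-SE imbalance, the shift is 0.5 × 0.2 × 9.43 = 0.94 points. Over baseline SD 20 to 40 and slope differences 0.05 to 0.2, the same formula gives 0.24 to 1.89 points.

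**5. Simulation without stratification** (36 per arm, SD 15, visit correlation 0.6, complete data, 4,000 trials each; pairs are without / with the term):

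| b28, b84 | Baseline SD | Empirical SE | Mean absolute shift | 97.5th percentile of shift | Coverage |
|---|---|---|---|---|---|
| −0.1, −0.1 | 30 | 3.55 / 3.55 | 0.10 | 0.44 | 0.949 / 0.948 |
| −0.05, −0.15 | 30 | 3.65 / 3.63 | 0.26 | 0.95 | 0.943 / 0.943 |
| 0, −0.2 | 30 | 3.68 / 3.61 | 0.53 | 1.69 | 0.945 / 0.945 |
| 0, −0.2 | 40 | 3.67 / 3.59 | 0.65 | 1.99 | 0.950 / 0.949 |
| −0.3, +0.1 (extreme) | 30 | 3.73 / 3.50 | 1.03 | 3.08 | 0.954 / 0.954 |

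The largest average bias in any row was 0.06 points. With equal slopes the extra term costs nothing visible.

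**6. Simulation with the planned stratification** (36 per arm, Screening values above 70 mg/dL, underlying SD 20, Screening-to-baseline correlation 0.85, complete data, 1,500 trials each):

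| r at Day 28 → Day 84 | SD of shift, simple | SD of shift, stratified | Variance ratio with / without, stratified |
|---|---|---|---|
| 0.75 → 0.70 | 0.17 | 0.12 | 1.001 |
| 0.8 → 0.6 | 0.52 | 0.41 | 0.984 |
| 0.8 → 0.5 | 0.82 | 0.61 | 0.969 |

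Allowing for simulation noise, the variance gain is 0 to 4%. The upper end also depends on the assumed Day 28 to Day 84 correlation, because a higher correlation raises w28.

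**The case against.** The strongest reply is that nothing is broken. Protocol, SAP text and code agree, and a common slope is a valid pre-specified choice under randomization. Parts of this stand:

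- **The slopes may be equal.** No section gives a between-visit correlation, a baseline SD or a visit-specific slope. Step 3 assumes a constant SD. If r fell from 0.8 to 0.6 while the Day 84 SD rose by 0.8/0.6 = 1.33, the slope would not move. A reader might infer that the planned model uses the wrong slope or biases the primary result. The documents support neither: the slope is wrong only if the two visits differ, and even then the error averages to zero over randomizations.
- **Stratification limits the imbalance.** It cut the SD of the shift by roughly a quarter in step 6. It uses two broad Screening categories, so imbalance within strata remains.
- **Sensitivity Analysis 2 already has a Day 84 slope.** True, and the SAP never says that this analysis isolates missing-data effects; Sensitivity Analysis 1 addresses missing data. But a supportive analysis does not remove the restriction from the headline estimate.
- **Not every MMRM is affected.** Protocol Appendix A schedules Lp(a) only at Visits 2 and 4. With one post-baseline visit the extra term is redundant.

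**Conclusion.** The point holds as an optional refinement. The primary MMRM carries a restriction that it does not need. Lifting it costs essentially nothing if the slopes are equal and gains a little precision if they differ. Under the planned stratification and the assumed correlations, the Day 84 estimate would move with an SD of about 0.1 to 0.6 points, with a variance gain of 0 to 4%. Only the deliberately extreme unstratified case, with slopes of opposite sign, goes clearly further: 1 − (3.50/3.73)² = 12% of variance.

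Against a 30-point planned effect and an SE of 3.54, the primary conclusion would not change; power stays above 99.99% even after a 7.5-point loss of effect. Type I error and coverage are not in question.

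The sizes rest on assumed baseline spread, correlations and effects, and the tabulated simulations used complete data. How a pooled slope would alter the borrowing from Day 28 when Day 84 is missing was not separately quantified.

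**What to change.** - In SAP 3.4.1, change the code to `model PCHG = TREATMENT VISIT TREATMENT*VISIT BASE BASE*VISIT / solution cl;` and add the baseline-by-visit interaction to the text.
- Use the same model after imputation in Sensitivity Analysis 1, in Sensitivity Analysis 4, in the ITT and PP runs, and in the secondary and exploratory MMRMs with two post-baseline visits (ApoB, non-HDL-C, VLDL-C, HDL-C, TG, ApoE). Leave Lp(a) out.
- Record the change in SAP Section 5. The protocol pre-specifies the same fixed effects, and that section now lists only changes to exploratory endpoints.

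The cost is one model term, one degree of freedom and one entry in Section 5. Sample size and power are unchanged. With complete data the primary contrast then equals the Sensitivity Analysis 2 estimate, so a gap between them would reflect missing data and not a different slope.
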